A SINGLE CENTRE EXPERIENCE OF LOCAL PERFORATOR FLAPS IN ONCOPLASTIC BREAST SURGERY; A CROSS-SECTIONAL STUDY

Date of document: 13th May, 2020

NCT Number: Not assigned

Approved by: ERC# 2020-3379-10190 of The Aga Khan University Hospital (AKUH)

Keywords: Local Perforator Flaps, Breast Cancer, Oncoplastic Breast Conserving Surgery, BREAST-Q, Breast Surgery

ABBREVIATIONS

LPF: Local perforator flap

BCS: Breast conservation surgery

OPS: Oncoplastic surgery

ICAP: Intercostal artery perforator

LTAP: Lateral thoracic artery perforator

DICAP: Dorsal intercostal artery perforator

LICAP: Lateral intercostal artery perforator

AICAP: Anterior intercostal artery perforator

IMF: Infra-mammary fold

ERC: Ethical Review Committee

AKUH: Aga Khan University Hospital

UOQ: Upper outer quadrant

LOQ: Lower outer quadrant

LIQ: Lower inner quadrant

INTRODUCTION

With breast cancer now presenting in earlier stages and the validation of several landmark trials confirming similar outcomes in women undergoing mastectomy versus breast conservation along with breast irradiation, more and more women are now candidates for a conservative approach [1,2]. Various techniques have emerged over the years for preservation of breast cosmesis without compromising the principles of tumor excision. One of such newer techniques for breast volume replacement after oncological surgery is the use of chest wall fasciocutaneous pedicled perforator flaps, such as the intercostal artery perforator flap (ICAP) and the lateral thoracic artery perforator flap (LTAP) for immediate partial breast reconstruction amongst few [4].

The use of a skin-muscle flap along with its intercostal neurovascular pedicle was first described in 1931 and has been in use since then for coverage of various surface defects [3,4]. The same principle utilizing the intercostal neurovascular pedicle or one of its perforators supplying the flap is now used for partial breast reconstructions with large defects with the preservation of underlying muscle [4,5]. This reduces the morbidity associated with muscle dissection. Based on the nutrient artery and the anatomic location of perforators, the intercostal artery perforator flaps (ICAP) can be classified as Dorsal intercostal artery perforator flap (DICAP) when the perforators arise from the vertebral segment of the intercostal vessels, Lateral intercostal artery perforator flap (LICAP) when the flap is based on perforators originating from the costal segment and Anterior intercostal artery perforator flap (AICAP) when the flap is based on perforators of anterior intercostal artery through the rectus abdominis or the external oblique muscles [4]. Hamdi et al reported the first use of LICAP flap in partial breast reconstruction for defects located in the lateral quadrants of the breast [5]. Losken et al described the use of AICAP flaps to cover defects over the inferior or medial quadrants of the breast due to its short pedicle [4,6].

Another newer option of a pedicled perforator flap for partial breast reconstruction is that of a Lateral thoracic artery perforator flap (LTAP) described by McCulley et al. This flap is based on single or multiple perforators arising from the lateral thoracic vessels. LTAP flap for breast reconstruction has advantage over other forms of pedicled perforator flaps; it has a secure vascular supply, has a transversely oriented scar which easily hides in the bra line, greater flap mobility and reach can be achieved with a narrow pedicle with minimal donor site morbidity and can also include LICAP perforators for better flap perfusion [7]. The perforators are identified by a hand held doppler preoperatively [4,5]. Both ICAP and LTAP flaps are considered safe and reliable for immediate partial breast reconstructions with good cosmetic outcomes and minimal morbidities as compared to traditional myocutaneous flaps [4,7].

Patient selection with good surgical technique following appropriate oncological principles is vital for safety and good outcomes of these flaps. These techniques have recently been adopted in our institution; therefore, the aim of this study is to report our initial clinical experience with pedicled perforator flaps in partial breast reconstruction along with cosmetic outcomes and patient satisfaction.

OBJECTIVES

1. To evaluate the surgical techniques of pedicled local fasciocutaneous perforator flaps (LPF) in partial breast reconstruction in terms of flap anatomy, location of perforators, operative time and post-operative morbidities in a tertiary care hospital of Pakistan.
2. To assess cosmetic outcomes and patient satisfaction following local perforator flaps in oncoplastic breast conserving surgery using the validated BREAST-Q BCT domain version 2.0.

METHODOLOGY

Study Design:

This will be a cross-sectional study.

Study Site and Data Collection Period:

All female patients who underwent a LPF for immediate partial breast reconstruction in the Breast section of The Aga Khan University Hospital will be included. For cosmetic outcomes and patient satisfaction, a follow-up of at least 3 months after surgery will be mandatory before participation in the survey.

ELIGIBILITY CRITERIA

Inclusion Criteria:

All female patients who underwent a LPF for immediate partial breast reconstruction at the breast surgery section of The Aga Khan University Hospital, Karachi will be included in the study.

Exclusion Criteria:

For evaluation of surgical techniques, since this is a review of cases already operated, there is no exclusion criteria.

For cosmetic outcomes and patient satisfaction, patients who have lost to follow, expired or not giving consent to participate in the study will be excluded.

STUDY OUTCOMES

Surgical techniques of pedicled local fasciocutaneous perforator flaps in partial breast reconstruction in terms of flap anatomy, location of perforators, operative time and post-operative morbidities will be collected on a pre-designed form by the researcher (Annexure 1). Cosmetic outcomes and patient satisfaction will be evaluated using BREAST-Q© version 2.0 BCT-module after a minimum of 3 months of surgery [8]. Satisfaction with breasts postoperatively and physical well-being with chest wall will be assessed (Annexures 2 and 4). Interpretation of both scales are provided as Annexures 3 and 5 respectively.

The BREAST-Q© is an established tool used to study the impact and effectiveness of breast surgery from patient's perspective and is the intellectual property of Drs. Andrea Pusic, Anne Klassen and Stefan Cano. The BREAST-Q© is owned by Memorial Sloan Kettering Cancer Center and The University of British Columbia (Copyright ©2012, Memorial Sloan Kettering Cancer Center and The University of British Columbia). It fulfills the Rasch and traditional psychometric criteria making it a new, cost-effective and analytic patient centered satisfaction measuring tool for breast surgery used worldwide [9]. License to use BREAST-Q© has been acquired. The scales have been translated in Urdu after seeking permission from the copyright holders. A stringent step by step translation guideline has been followed using an excel sheet workbook provided by the authors involving 3 translators and cognitive debriefing has been performed with 5 patients. The Urdu translation of both scales in Annexures 2 and 4 is provided as Annexures 6 and 7 respectively along with their corresponding interpretations.

DATA COLLECTION

Data on flap dimensions, location of perforators, location of tumor and its size, size of breast defect after tumor excision, operative time, number and duration of drains placed, duration of hospital stay and any morbidity will be collected by a member of research team from patient's medical records. Location of perforators will be determined in relation to the breast meridian, infra-mammary fold and lateral breast curve as defined by the primary surgeon. Data will be collected on a pre-designed form by the researcher (Annexure 1). Patients will fill the questionnaires for cosmetic outcomes and satisfaction only once during their routine follow-up in clinic after a minimum of 3 months of surgery (Annexures 2 and 4 for English, Annexures 6 and 7 for Urdu) which will require less than 10 minutes of their time. Hard copies of the data will be stored in a locked cupboard of primary researcher's office after entering in SPSS. Data will be stored with the primary researcher for 7 years after completion of study.

ETHICAL CONSIDERATIONS

Approval to conduct the study is taken from the Departmental Review Committee (DRC) and institutional Ethical Review Committee (ERC) of The Aga Khan University Hospital, Karachi. Patients will be approached for 2 consents: one for their cosmetic outcomes and satisfaction survey and second for the pictures of their breasts. Written and informed consent in English or Urdu will be obtained by the researcher (PI / co-PI) in breast clinic from all study subjects visiting AKUH for their routine follow-up for the patient satisfaction survey after explaining them the purpose of study (Annexure 8 and 10). Hard copies of the proformas will be handed over to them in their preferred language (English or Urdu) after their agreement to participate (Annexures 2 and 4 for English, Annexures 6 and 7 for Urdu). Patients will select the most appropriate answers from the list of provided options for themselves. If any patient is unable to read, her attendant will assist her, otherwise the researcher will read the questions and their options to her one by one. A separate consent for breast photographs of selected cases will also be taken by PI / co-PI at the same time (Annexures 9 and 11). The pictures will demonstrate tumor location, flap designs and final outcomes of breasts and scars for publication after concealing all patient identifiers. The patients can refuse for photographic consent and still participate in the satisfaction survey. Pictures of consenting patients will be taken in breast clinic's treatment room by PI following a standard protocol i.e., bilateral front, oblique and lateral views and shown to patients before finalization. All unnecessary / out of focus pictures will be immediately deleted. No identification marks will be included in the pictures. All pictures will be coded

and stored in a password protected folder / passport drive in PI's office desktop along with other data from the study for 7 years. The process of obtaining consent will take 2 to 3 minutes.

Use of the BREAST-Q Questionnaire, authored by Drs. Klassen, Pusic and Cano, was made under license from Memorial Sloan Kettering Cancer Center, New York, USA.

ANALYSIS

The analysis will be done on Statistical Package for Social Sciences (SPSS version 24). Descriptive quantitative variables such as operative time will be reported as mean \pm SD/ median (IQR) depending upon the normality of the data. For qualitative variables such as location of perforators, flap dimension, cosmetic outcomes and patient satisfaction, frequency and percentages will be reported. Content validation index (CVI) will also be reported.

STRENGTHS OF THE STUDY

This study is a review of our initial clinical experience with pedicled perforator flaps in partial breast reconstruction which has been recently adopted in our institution. No work on pedicled perforator flaps in partial breast reconstruction has been published from Pakistan as yet to the best of our knowledge.

LIMITATIONS OF THE STUDY

Single institution experience with limited number of cases will limit the generalizability of the study results.

STUDY IMPLICATIONS

This study will determine the technical outcomes of a relatively new partial breast reconstruction technique which will help in disseminating the knowledge from our part of the world and will help in training more surgeons for adapting this skill for our women population. It will also evaluate the patient's perspective and help in improving our techniques if any shortcomings are identified.

REFERENCES

3. Esser J. Biological or artery flaps of the face. Monaco: Institut Esser de Chirurgie Structive; 1931.

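### Does the morbidity outcome need a written time window and a rule for records that stop early?

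*Combined protocol and SAP*

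**What the plan says.** Post-operative morbidity is one of the four components of objective 1, with flap anatomy, perforator location and operative time. The Study Outcomes section says that "operative time and post-operative morbidities will be collected on a pre-designed form by the researcher (Annexure 1"). Data Collection lists morbidity beside drains and hospital stay: "duration of hospital stay and any morbidity will be collected by a member of research team", with the medical record as the source.

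The population for this part is every operated case. The Exclusion Criteria state: "For evaluation of surgical techniques, since this is a review of cases already operated, there is no exclusion criteria".

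The follow-up rules are written for the other objective. Under Study Site and Data Collection Period: "For cosmetic outcomes and patient satisfaction, a follow-up of at least 3 months after surgery will be mandatory before participation in the survey". Under Exclusion Criteria, again for cosmetic outcomes and satisfaction only, "patients who have lost to follow, expired or not giving consent to participate in the study will be excluded". Data Collection adds that patients complete the questionnaires "only once during their routine follow-up in clinic after a minimum of 3 months of surgery".

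The Analysis section says of qualitative variables that "frequency and percentages will be reported". Morbidity is not among its examples. Under Limitations, the authors write: "Single institution experience with limited number of cases will limit the generalizability of the study results".

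**The concern.** Of the four components of objective 1, only morbidity depends on how long the patient is observed; the other three are settled by the end of the operation. The protocol ties the survey to a minimum follow-up and says who is left out of it, but has no counterpart for morbidity. On the body text alone, a patient operated on shortly before chart review, or lost soon after discharge, enters the denominator beside patients followed for many months. If her chart shows no event, she counts as event-free by default. A late event in a long record counts too. The resulting percentage would refer to no stated period and would be hard to set beside another series. This is a study meant to report the technical outcomes of a newly adopted procedure and to help train surgeons in it.

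**Working it through.** **Is there a figure to reproduce?** No. The documents state no sample size, expected morbidity, event count, participation rate or calendar dates. Every number below except the 3-month survey minimum is an assumption or follows from one.

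**Reading the sections together.**
- Numerator: events found in the medical record, entered on Annexure 1.
- Denominator: all operated cases, since this part has no exclusions.
- Window: none in the body text. Annexure 1 was not available, and a list of complications, dates or a window would normally sit on such a form.
- Summary: frequency and percentage, by inference, because the Analysis section introduces its qualitative variables as examples and does not name morbidity.

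The plan therefore has a numerator source and a denominator. What the body text lacks is a time reference.

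**Effect of records that stop early.** Let p90 be the true 90-day morbidity, s the share of records that stop early, and f the fraction of 90-day events already charted when they stop. Then

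crude % = p90 × [(1 − s) + s × f].

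With p90 = 20%:
- s = 10%, f = 0.8: 20% × (0.90 + 0.08) = 19.6%
- s = 20%, f = 0.5: 20% × (0.80 + 0.10) = 18.0%
- s = 40%, f = 0.3: 20% × (0.60 + 0.12) = 14.4%

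The shortfall runs from 0.4 to 5.6 percentage points. The ratio to the true 90-day figure is 0.72 to 0.98 whatever p90 is.

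**Effect of late events.** Suppose 30 cases, 3 with an event inside 90 days. One or two later events in longer charts turn 3/30 = 10.0% into 4/30 = 13.3% or 5/30 = 16.7%. This pushes the other way, so the net direction is open.

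**Upper bound on the uncertainty.** Let n be the cases operated on at least one window before extraction, x those with an in-window event, and u those with no such event who were not observed to the end of the window. The in-window proportion lies between x/n and (x + u)/n. If charts are read on or after the survey visit, participants are observed to at least 3 months, so u cannot exceed the eligible cases not surveyed. With n = 30 and x = 3, 90% participation gives u ≤ 3 and a range of 3/30 = 10% to at most 6/30 = 20%. At 70%, u ≤ 9 and the top is 12/30 = 40%. At full participation the width is zero. These are maxima. They need every non-surveyed patient to be unobserved and every one of them to have had an event, although a patient who declines a questionnaire may still have clinic notes. They also assume an order of chart review and survey that the documents do not give.

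**Would a stricter rule do better?** One option is to restrict the morbidity denominator to patients with a full window before data extraction. Suppose 3 of 30 cases are too recent, and one of the 3 events fell in that group. The all-cases figure is 3/30 = 10.0%; the restricted figure is 2/27 = 7.4%, and a real early complication leaves the rate. In a small first-experience series that is a loss, and it departs from the all-cases design.

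**Would an exact interval help?** The Clopper-Pearson 95% interval is 2.1% to 26.5% for 3/30, and the upper limit for 0/30 is 11.6%. These widths come from the number of cases. They do not measure, or repair, a missing window.

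**The case for a change.** The strongest case for a change is that the omission is real, concerns a named component of an objective and would be cheap to close: a few lines of wording, plus the dates of surgery, last visit and any event from charts already under review. The survey rules show that the authors knew follow-up matters. Even if Annexure 1 sets a window, the Analysis section still does not say how a short record is counted. With few cases, a report of no complications could be over-read.

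Much of this stands. The body text gives no window and no short-record rule, and a reader of the results will want to know how long patients were followed. What does not follow is that the plan yields a wrong or misleading result. That needs several steps that the documents do not show: that Annexure 1 sets no window, that an appreciable share of charts stop early, that events fall after they stop or that late events are counted in, and that the report says nothing about follow-up. The protocol describes cases already operated, which suggests that much of the follow-up may have elapsed, though it gives no dates. Listing morbidity beside drains and hospital stay makes a peri-operative reading plausible, though no limit is stated. The point about over-reading concerns precision, which is a matter of case numbers; the authors already concede that these are limited, though they do so only for generalizability.

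**Conclusion.** No change to the plan is called for. The body text leaves out a detail that an analyst of a descriptive chart review would ordinarily supply: report recorded events over all operated cases, give each event's timing, state follow-up length, and say how many records are short. All of this can be read from the charts the study already uses, and none of it needs a different design or denominator.

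The size of any distortion cannot be derived from the documents. The illustrations run from a shortfall of 0.4 to 5.6 percentage points on a true 20% to an overstatement of a few points if late events are counted, all on assumed inputs; no bias is shown in either direction. No test, comparison or decision depends on the figure.

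This rests on two assumptions: that Annexure 1 does not contradict the body text, and that the report describes follow-up as such series usually do. Restricting the denominator to patients with a full window would bring a drawback of its own, and exact intervals, though harmless, would address a different question.

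### The ANALYSIS section treats flap dimension and the BREAST-Q outcomes as qualitative variables reported by percentages, which omits level and spread unless the annexures define categories

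*Combined protocol and SAP*

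**What the plan says.** The ANALYSIS section has two reporting rules. For numerical data: "Descriptive quantitative variables such as operative time will be reported as mean" with SD, or as median with IQR, according to normality. For the rest: "For qualitative variables such as location of perforators, flap dimension, cosmetic outcomes and patient satisfaction, frequency and percentages will be reported". The only other statistic it mentions is a content validation index, which is not a summary of patients' results.

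The other sections say what these variables are.

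- **Flap dimension.** DATA COLLECTION lists what is taken from the records: "Data on flap dimensions, location of perforators, location of tumor and its size, size of breast defect after tumor excision", followed by "operative time, number and duration of drains placed, duration of hospital stay and any morbidity will be collected". The recording form is Annexure 1.
- **Cosmetic outcomes and satisfaction.** STUDY OUTCOMES assigns these to the BREAST-Q version 2.0 BCT module and then names two scales: "Satisfaction with breasts postoperatively and physical well-being with chest wall will be assessed". It adds: "Interpretation of both scales are provided as Annexures 3 and 5 respectively". The same section says of the Urdu versions: "The Urdu translation of both scales in Annexures 2 and 4 is provided as Annexures 6 and 7 respectively along with their corresponding interpretations".
- **How patients respond.** ETHICAL CONSIDERATIONS says: "Patients will select the most appropriate answers from the list of provided options for themselves".

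**The concern.** A flap dimension is by name a measurement, and it is collected in the same list as operative time. The plan gives operative time a mean or median with its spread but calls flap dimension qualitative. No size categories appear in the text available.

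The two BREAST-Q scales are the stated measure for the second objective. The plan calls them scales and supports the choice of instrument by its Rasch and traditional psychometric properties. Yet the reporting rule is percentages, with no statement of whether these are percentages of item answers, of score bands or of individual scores. The rule's two labels, cosmetic outcomes and patient satisfaction, do not map one to one onto the two scales, and physical well-being is not mentioned in the ANALYSIS section.

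At stake is how fully the study describes its own results. A reader would want the typical score on each scale and how much patients differ. A surgeon learning the technique would want a typical flap size and its range. LIMITATIONS OF THE STUDY expects few cases, so it is worth keeping the recorded values.

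**Working it through.** The plan states no figure on this point, so there is nothing to reproduce. The check sets the sections side by side and asks what each possible kind of percentage would retain.

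**Step 1: flap dimension.** DATA COLLECTION puts it beside tumor size, defect size and operative time. The ANALYSIS section puts operative time under mean ± SD or median (IQR) and flap dimension under percentages. No available text explains the difference. Only categories on Annexure 1 would.

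**Step 2: which scales the percentage rule covers.** STUDY OUTCOMES names two scales; the ANALYSIS section names 0 of 2. Two readings are possible.

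- The phrase for cosmetic outcomes and satisfaction is the plan's label for both questionnaires. DATA COLLECTION supports this, because it uses similar words for Annexures 2 and 4 together. Then both scales are under percentages.
- The phrase does not reach physical well-being. Then that scale is unclassified, and the open rule for quantitative variables could apply to it.

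Under either reading, no available text states a summary of level and spread for either scale (0 of 2). Under the second, such a summary for physical well-being is unstated but not excluded.

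**Step 3: what each kind of percentage retains.**

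*Item answers.* These do not fix the spread of a score, because they do not show which answers occur together in one patient. A logical illustration, not study data: two patients answer two items, each scored 1 or 2.

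| Case | Patient A | Patient B | Totals | Mean | SD |
|---|---|---|---|---|---|
| 1 | (1, 1) | (2, 2) | 2 and 4 | 3 | 1.41 |
| 2 | (1, 2) | (2, 1) | 3 and 3 | 3 | 0 |

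In case 1, SD = √{[(2 − 3)² + (4 − 3)²] / (2 − 1)} = √2 = 1.41. In case 2, SD = √{[(3 − 3)² + (3 − 3)²] / (2 − 1)} = 0. In both cases each item has 50% answering 1 and 50% answering 2. The item percentages are identical, but the spread of the total differs.

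*Score bands.* These convey level and spread coarsely and discard the values within each band. The available text gives no cut-points.

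*Every individual score.* A full frequency table would let a reader work out the mean and SD. The plan does not say that this is meant.

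The illustration applies to item percentages only; it says nothing against the other two.

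**The case against.** The strongest reply is that the material needed to judge the rule is in annexures that were not available. Annexure 1 may record flap dimension in categories. Annexures 3 and 5, and the interpretations supplied with Annexures 6 and 7, may define bands. Patients choose among listed options, so percentages of answers are a legitimate summary, and frequencies of ordered categories do carry some information on level and spread. No available text describes a numerical scale score; the reference to Rasch criteria is the nearest indication. In a small descriptive series, the choice of summary may also be partly a matter of preference.

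Most of this stands, and it limits the conclusion. If Annexure 1 uses categories, the flap point falls away. Bands would make percentages valid for the scales. They would still lose the values within each band, so reporting the score as well would remain an improvement wherever a score exists.

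Three stronger readings are tempting, and the documents do not support them.

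- A reader might infer that the plan never names the scales. STUDY OUTCOMES names both; only the ANALYSIS section does not.
- A reader might infer that the other numerical record items, such as tumor size or hospital stay, have no planned summary. The quantitative rule is open-ended, with operative time as an example, and covers them. Only flap dimension is expressly placed elsewhere.
- A reader might infer that the planned percentages are wrong or that the second objective cannot be answered. They are a valid but incomplete report.

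**Conclusion.** The point holds as a minor one, with moderate confidence. The ANALYSIS section expressly classes flap dimension, cosmetic outcomes and patient satisfaction as qualitative. This is a stated rule and not merely missing detail. It sits poorly with the way flap dimensions are collected and with the use of two named scales.

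The conclusion assumes that flap dimensions are recorded as numbers and that each scale yields a score. Both are likely from the wording, but the annexures could show otherwise.

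No numerical size of effect can be derived from the documents, and none is claimed. The consequence is limited: nothing is tested or decided on these summaries, the data are kept for 7 years, and the omission can be repaired at analysis.

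**What to change.** Revise the sentence on qualitative variables in the ANALYSIS section.

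1. Report satisfaction with breasts and physical well-being (chest wall) separately and by name. For each, give the number of respondents and the mean ± SD or median (IQR) of the scale score. The number matters because patients lost to follow-up, deceased or not consenting are excluded from the survey but not from the surgical review.
2. Keep percentages of item answers or bands as a supplement, and state which they are.
3. Move flap dimensions, where recorded as numbers, to the mean ± SD or median (IQR) rule already used for operative time. If Annexure 1 records categories, say so and leave them under percentages.
4. Keep frequency and percentages for nominal variables such as perforator location.

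The cost is two or three sentences and a little more analysis work, with no new data and no additional patients.

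### Does the analysis section promise a content validation index that the study has no data to compute?

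*Combined protocol and SAP*

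**What the plan says.** The index is mentioned once, in the ANALYSIS section: "Content validation index (CVI) will also be reported". It comes after the descriptive summaries (mean with SD or median with IQR for quantitative variables, counts and percentages for qualitative ones). It does not appear under OBJECTIVES, STUDY OUTCOMES or DATA COLLECTION.

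The BREAST-Q paragraph at the end of STUDY OUTCOMES describes the Urdu translation of the two scales as already completed. A guideline was followed with an Excel workbook supplied by the instrument's authors, "involving 3 translators and cognitive debriefing has been performed with 5 patients". On the patients' side, DATA COLLECTION says: "Patients will fill the questionnaires for cosmetic outcomes and satisfaction only once during their routine follow-up in clinic".

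**The concern.** A content validity index is the share of raters who judge an item relevant, sometimes averaged over the items of a scale. It needs relevance ratings from identified raters. Patients who complete the BREAST-Q report on their own breasts and chest; they do not judge whether the items are relevant. Answers to the questionnaire therefore cannot supply the index.

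The plan names no raters, no relevance scale and no form on which ratings would be entered. The team might then have to drop a listed result or take it from a source that the plan does not describe. A reader might also take an unexplained value as evidence that the Urdu version is valid, and the Urdu version carries the second objective for the patients who use it.

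**Working it through.** There is no stated figure to reproduce: the plan gives no value, threshold or formula for the index. The check is a comparison of the text with itself.

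**Step 1. What each cited annexure is described as holding.**

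| Annexure | Described content | Section |
|---|---|---|
| 1 | Surgical data form, filled from medical records | STUDY OUTCOMES; DATA COLLECTION |
| 2, 4 | The two English scales | STUDY OUTCOMES |
| 3, 5 | Interpretation of those scales | STUDY OUTCOMES |
| 6, 7 | The two Urdu scales, with interpretations | STUDY OUTCOMES (BREAST-Q paragraph) |
| 8, 10 | Survey consent | ETHICAL CONSIDERATIONS |
| 9, 11 | Photograph consent | ETHICAL CONSIDERATIONS |

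Count: 1 + 2 + 2 + 2 + 2 + 2 = 11. None is described as a relevance-rating form. The plan's own words for two of the pairs are "Interpretation of both scales are provided as Annexures 3 and 5 respectively" and "The Urdu translation of both scales in Annexures 2 and 4 is provided as Annexures 6 and 7 respectively".

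**Step 2. What that count can show.** Less than it seems. The annexures are not reproduced in the available text, so only their short descriptions can be read. Six of the 11 are consents (4) or interpretation sheets for the English scales (2), where nobody would look for ratings. Four more are the patient scales, and the last is the surgical form. The document most likely to hold ratings is the translation workbook, and it is not a numbered annexure. The count therefore does not test the likeliest source.

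**Step 3. Whether the text rules out a source.** It does not. The ANALYSIS section says that the index will be reported; it does not say that ratings will be collected. A completed translation exercise with translators and debriefed patients is a plausible origin for such an index. The text neither confirms nor excludes this.

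**Step 4. Whether the number of raters matters for reading a value.** Assume, without support in the documents, that the people in the translation step were the raters. With one rater of n dissenting, the item-level index is (n − 1)/n:

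- n = 3 translators: 2/3 = 0.67
- n = 5 patients: 4/5 = 0.80
- n = 3 + 5 = 8: 7/8 = 0.88

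With no dissent it is 1.00 in each case. This shows that a published index should come with its number of raters. It does not measure any error in the study's results.

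**Step 5. What depends on the index.** Objective 1 covers flap anatomy, perforator location, operative time and morbidity, taken from records. Objective 2 covers cosmetic outcome and satisfaction, taken from the BREAST-Q answers. Neither uses the index as an input, a selection rule or a threshold.

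**The case for a change.** The best case for a change is that the analysis is purely descriptive, so each listed statistic should have a traceable source, and this one has none stated. The repair would be a single sentence: complete it if ratings were recorded, delete it if they were not. The possible misreading of an unexplained index as validation of the Urdu scales adds some weight.

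The factual part stands. The instrument, raters, rating scale, form of index and source are all unstated, and the text does not link the translation work to the index. The claim that no source exists does not stand, because the likeliest source cannot be inspected. Two feared consequences are also unsupported. Nothing in the plan suggests deriving the index from satisfaction answers. Nothing suggests collecting new ratings from patients either, so whether the two consents would cover that step does not arise.

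The repair would fill in a description or remove a sentence. It offers no better method and alters no estimate. The risk of misreading arises at publication, where the authors would in any case have to say who rated what.

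**Conclusion.** The gap is real but it is one of reporting detail, and it calls for no change to the plan. The plan lists a content validation index without its instrument, raters, scale, form or source. Zero of the 11 annexures is described as holding the ratings, but the completed Urdu translation work remains a possible source. The effect on the flap and satisfaction results is nil, because the index enters none of them. Analysts who hold ratings can report the index with its raters and form; analysts who hold none have no index to report, and both objectives are untouched. This conclusion rests on the descriptions of the annexures and of the translation step, since neither the annexures nor the workbook could be read.
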